10.3. Reporting of Suspected Unexpected Serious Adverse Drug Reactions (SUSARs)

It is the duty of the KKS to report in accordance with legal requirements *fatal or life threatening* SUSARs within 7 calendar days and *non-fatal and non-life threatening* SUSARs within 15 calendar days after receiving first notification of the event to the Ethics Committee, Competent Authorities and all participating investigators.

10.4. Assessment of causality of adverse events / reactions

The relationship of adverse events to the medicinal products being studied should be determined according to the classification below:

certain:

- Event or laboratory test abnormality, with plausible time relationship to drug intake
- Cannot be explained by disease or other drugs
- Response to withdrawal plausible (pharmacologically, pathologically)
- Event definitive pharmacologically or phenomenologically (i.e. an objective and specific medical disorder or a recognized pharmacological phenomenon)
- Rechallenge satisfactory, if necessary

probable:

- Event or laboratory test abnormality, with reasonable time relationship to drug intake
- Unlikely to be attributed to disease or other drugs
- Response to withdrawal clinically reasonable
- Rechallenge not required

possible:

- Event or laboratory test abnormality, with reasonable time relationship to drug intake
- Could also be explained by disease or other drugs
- Information on drug withdrawal may be lacking or unclear

unlikely:

- Event or laboratory test abnormality, with a time to drug intake that makes a relationship improbable (but not impossible)
- Disease or other drugs provide plausible explanations

not related:

- no causal relationship

not assessable:

- Report suggesting an adverse reaction
- Cannot be judged because information is insufficient or contradictory
- Data cannot be supplemented or verified

not applicable:

- If any of causal relationship does not make sense (e. g. exposure during pregnancy, overdose, medication error)

unknown:

- no information is available

11. *Statistical Considerations*

11.1. *Description of analysis sets*

Intention to treat set (ITT)

The ITT set includes all patients who were randomized regardless of whether they received treatment or not. Patients will be analysed in the treatment group they were randomized to, regardless of whether they were treated in this group or not.

Per-protocol set (PP)

The PP set includes the patients of the corresponding ITT-set for whom no major protocol violations occurred. A compilation of the major protocol deviations will be generated by the coordinating investigator.

Safety Set

The safety set of the study consists of patients who received at least one dose of sorafenib or placebo and for whom post-dose data are available. Patients will be analysed in the

treatment group they were treated in, regardless of whether they were randomized to this group or not.

11.2. Power and Sample Size Calculation

The primary endpoint of the study, relapse-free survival (RFS), is defined as the time interval from randomization until relapse or death from any cause, whichever occurs first. For a patient with none of these events before the end of study follow-up, observation of RFS will be censored at the date of his or her last follow-up examination. It is assumed that the RFS rate after 2 years may be increased from 65% with placebo (Gale et al., Blood 2005; Thiede et al., Blood 2006) to 82.5% with sorafenib, corresponding to a hazard ratio (HR) of 0.45. Comparing the sorafenib with the placebo group by a log-rank test at a two-sided alpha of 5%, 49 observed events are required to obtain a power of 80%. It is important to note that due to a decreasing likelihood of relapses over time, the Kaplan-Meier curve for RFS of Flt3-ITD AML patients after allo-SCT forms a plateau after around 2 years at the above-mentioned values.

Under these assumptions, 184 patients (i.e., 92 per group) are needed in order to observe 49 events after a minimum observation period of 24 months for each patient. The inclusion of a total of 200 patients in the study allows for compensation of a dropout rate of 8%. During the course of the study, it may be decided to adapt the number of included patients. If this is done based on a data inspection (rather than solely on the absolute number of events which occurred so far, irrespective of the study arm), the method for sample-size adaptation in survival trials developed by Schäfer and Müller (Schäfer H, Müller H-H. Modification of the sample size and the schedule of interim analyses in survival trials based on data inspections. Statist Med 2001;20:3741-3751) will be employed which ensures that the type I error risk is not affected. It may also be decided later to add one or more interim analyses using the adaptive method mentioned above, especially if the sample size is increased.

11.3. Interim analysis

There will be an interim analysis of safety after 20 patients have been treated for at least 3 months. Numbers of adverse events will be analyzed descriptively as well as in comparison between the two study arms by means of Fisher's exact test. An interim data inspection will be performed during the first half of 2014 according to the method proposed by Schäfer and Müller (Statist Med 20:3741-3751, 2001), which will take into account all patients included in the SORMAIN trial so far. This will offer the study management the chance to adapt the total sample size while keeping the original type I error rate constant, that is, without increasing the risk of a false positive study result. The reasons for this interim data inspection, which

had not been explicitly planned but outlined in the study protocol (V03F, Section 11.2 Power and Sample Size Calculation, p.44) to be decided about later, are twofold:

- (1) The recruitment rate has been much lower than expected. Whereas 200 patients were planned to be recruited within an accrual period of 24 months, only 45 patients have been randomized after 40 months of accrual.
- (2) Based on accumulating evidence from controlled trials with AC220 and Midostaurin (both are new FLT3-ITD inhibitors) and clinical experience with sorafenib used outside of clinical studies in the AML indication, it is not unlikely that sorafenib therapy might generate a larger treatment benefit compared to placebo than the hazard ratio of 0.45 implies, which was originally assumed for the sample size calculation.

If the interim data inspection, which takes into account all available information regarding relapse or censoring events as well as treatment group allocation of patients, shows indeed a larger treatment difference than originally assumed, the additional number of events required before the final analysis, and hence the sample size, could be reduced. This would enable completion of the SORMAIN trial and a judgement of efficacy in less time and with a smaller number of patients.

According to the method by Schäfer and Müller, the data obtained up to the time point of the interim inspection will be used to calculate the value of the log-rank test statistic. Given that value, the probability of falsely rejecting the null hypothesis of no treatment difference (conditional rejection error probability, CRP) at the originally planned study end point, that is, after a total number of 50 events, will be calculated using the formulae in the above-mentioned paper. The design of the remaining part of the trial can be changed to any other design, that is, to a different number of additional events up to the final analysis, with the log-rank test statistic finally being applied to the additional events and assuming a type I error rate equal to the CRP calculated at the interim inspection. It is allowed to use all information from the interim inspection, such as Kaplan-Meier curves and estimates of the treatment difference (hazard ratio), to recalculate the additional number of events required to obtain a given power, without the total type I error being compromised. It is even possible to apply a group-sequential design to the remaining part of the trial. Alternatively, it can be decided after the interim inspection to leave the trial design unchanged.

The preservation of the pre-specified type I error rate – in this trial a two-sided alpha of 0.05 – is guaranteed when applying the CRP principle if the interim data inspection is used for sample-size adaptation only but not for an interim analysis with the option to reject the null hypothesis of no treatment difference. It is hereby explicitly stated that the envisaged interim inspection will not be used to perform such an analysis, that is, no formal statistical test will be done at that interim time point with the chance to conclude that a significant treatment difference is present. In other words, no alpha will be spent at the interim inspection.

In order to perform the interim data inspection, the trial biostatistician will receive the data regarding relapse and censoring events together with treatment group membership, that is, in a blinded fashion, without any further variables. The Coordinating Centre for Clinical Studies (KKS) Marburg will provide these data with new random ID numbers, such that the biostatistician can use as little information from the interim inspection as possible at later stages of the analysis, maintaining blinding to the largest possible degree. The results of the interim data inspection (log-rank test statistic, CRP given the test statistic, Kaplan-Meier curves, treatment difference in terms of hazard ratio) as well as recalculated power values assuming the CRP and various effect sizes will be communicated by the biostatistician only to the unblinded contact. The unblinded contact will communicate in an unblinded fashion with the DSMC members. The DSMC will decide about whether and how the design of the remaining part of the trial should be changed, e.g. the sample size reduced in case of an unexpectedly large treatment difference, or whether the trial should be stopped due to futility. This decision will be communicated in written form to the unblinded contact and the Steering Committee. If the design is modified, this will be specified in a further protocol amendment. The details of a design modification will be communicated to as few people involved in the performance of the trial as possible, in order to avoid that study personnel might draw conclusions about the observed treatment difference from the decision regarding the change of trial design.

11.4. *Statistical Analysis Plan*

The primary objective, RFS (as defined above), will be analyzed by means of the Kaplan-Meier method as well as the log-rank test at a two-sided alpha of 0.05 to test for differences between the two study arms. Possible sample size modifications or interim analyses will be performed according to the adaptive method by Schäfer and Müller as described in section 11.2.

Secondary endpoint of the study is overall survival (OS), defined as time from randomization to the day of death; for a patient who is not known to have died by the end of follow-up,

observation of OS will be censored on the date the patient was last known to be alive. This and other secondary objectives will be analyzed by the Kaplan-Meier method and the log-rank test. Furthermore, RFS and OS will be analyzed by Cox regression in order to account for prognostic factors (Flt3-ITD ratio at diagnosis, treatment with Flt3-inhibitors before allogenic stem cell transplantation, occurrence of chronic GvH). The analysis will be performed according to the intention-to-treat principle.

With regard to safety, numbers of adverse events will be analyzed descriptively as well as in comparison between the two study arms by means of Fisher's exact test.

12. Efficacy

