4.1. Objectives

4.1.1. *Primary objective*

Relapse free survival (RFS) of Flt3-ITD+ AML patients in complete hematological remission after allo-SCT receiving Sorafenib maintenance therapy versus placebo

4.1.2. *Secondary objectives*

- To compare the median overall survival (OS) of Flt3-ITD+AML patients in CHR after allo-SCT receiving Sorafenib maintenance treatment versus placebo
- To compare the median RFS and OS of Flt3-ITD+ AML patients with and without NPM mutations receiving Sorafenib versus placebo
- To compare the median RFS and OS of Flt3-ITD+AML patients in CHR after allo-SCT receiving Sorafenib maintenance treatment versus placebo depending on the baseline expression level of Flt3-ITD at diagnosis
- To compare the toxicity of Sorafenib maintenance versus placebo
- To longitudinally evaluate biomarkers associated with Sorafenib treatment response and Sorafenib resistance and correlation with RFS and OS
- To assess safety with type, severity graded by NCI CTC criteria version 4.02.

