5.1. Study population

200 patients aged ≥ 18 years with Flt3-ITD positive AML, who have undergone allo-SCT

- for chemotherapy-refractory disease,
- or for consolidation in first or second complete remission

will be treated with either placebo (control group) or Sorafenib (verum group) to maintain a CHR and to prevent hematological relapse.

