5.2. Inclusion criteria

- Written informed consent
- Age ≥ 18 y.
- ECOG performance ≤ 1
- FLT3-ITD-positive AML
- Complete hematological remission (CHR) after allo-SCT
- CHR must be confirmed by bone marrow analysis within 14 days before randomization (CHR criteria are: $\leq 5\%$ marrow blasts, no peripheral blasts, blood platelet count $> 100/\text{nl}$, WBC count $> 3 \text{ G/L}$, ANC $> 1 \text{ G/l}$).
- Allo-SCT with a HLA-identical allo-family donor (FAM) or a matched unrelated donor (MUD) with up to 1 antigen mismatch acceptable (9/10)
- Time point of study treatment start of patients in CHR: between d+60 up to d+100 after allo-SCT
- Adequate organ function:

-
- Serum creatinine ≤ 1.5 x upper normal value
 - ALT, AST, AP ≤ 2.5 x upper normal value
 - Total bilirubin ≤ 1.5 x upper limit of normal
 - PT-INR/PTT ≤ 1.5 x upper limit of normal
 - Patients who are being therapeutically anticoagulated with an agent such as Coumadin or Heparin will be allowed to participate provided that no prior evidence of underlying abnormality in these parameters exists)
 - Negative serum pregnancy test within seven days prior to first dose in women of child-bearing potential (WOCBP)
 - WOCBP must use a double barrier method of contraception during the study and for 3 months following the last dose of study drug. WOCBP are defined as sexually mature women who have not undergone a hysterectomy or surgical sterilization or who have not been naturally postmenopausal for at least 12 consecutive months (i.e., who has had menses any time in the preceding 12 consecutive months).
 - Male subjects whose sexual partners are WOCBP must use a double barrier method of contraception, one of which includes a condom, during the study and for 3 months after the end of treatment.

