- **Donor lymphocyte infusions (DLI) are not part of this trial, and are generally not planned**, because there is no experience regarding the potential of Sorafenib to aggravate a graft versus host response in the context of DLI. Sorafenib may alter the activation and function of immunologically relevant cellular sub-fractions and thus the efficacy, tolerability and side effects (elicitation of GvHD) of DLI. DLI may, however, be performed at the discretion of the treating physician.

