12.2. Definition of Study Endpoints

12.2.1. Primary endpoint

=> Relapse Free Survival (RFS), 50 events (relapse)

RFS is defined as time interval from randomization until relapse of AML or death from any cause, whichever ever occurs first. Relapse is defined as any blast appearance in the peripheral blood, in the bone marrow (> 5%) or extramedullary blasts (chloroma). For a patient with no relapse before the end of study follow-up, observation of RFS will be censored at the date of his or her last follow-up examination.

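### Section 11.4 adjusts the supportive Cox models for chronic GvHD, which can arise after randomisation; if sorafenib changes it, the adjusted hazard ratio is not the intention-to-treat effect

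*Protocol*

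**What the plan says.** Protocol section 11.4 tests RFS by an unadjusted log-rank test at a two-sided 5% level and analyses OS by Kaplan-Meier and log-rank. It then adds that "RFS and OS will be analyzed by Cox regression in order to account for prognostic factors". It names three such factors: the Flt3-ITD ratio at diagnosis, and "treatment with Flt3-inhibitors before allogenic stem cell transplantation, occurrence of chronic GvH". The next sentence reads "The analysis will be performed according to the intention-to-treat principle".

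The clock starts at randomisation. Section 12.2.1 states that "RFS is defined as time interval from randomization until relapse of AML or death from any cause", and OS also runs from randomisation. Patients are randomised after the baseline screen and then start therapy (section 7.1). Section 5.2 places that start after transplant: "Time point of study treatment start of patients in CHR: between d+60 up to d+100 after allo-SCT". Section 5.3 excludes patients with active, uncontrolled GvHD above grade I at randomisation.

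Three places bear on whether the drug can affect this pathway. Section 3.4 says experience of sorafenib's interference with GvL and GvHD is limited. Section 6.1.2.3, on donor lymphocyte infusion, says "Sorafenib may alter the activation and function of immunologically relevant cellular sub-fractions" and mentions elicitation of GvHD. Section 3.3 presumes synergism between sorafenib and the GvL effect.

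**The concern.** A covariate helps to estimate a randomised treatment effect if its value is fixed before treatment can influence it. Two of the three listed factors meet that condition. Chronic GvHD, as worded, does not: a patient free of it at randomisation can develop it on sorafenib or placebo, and is then classified by something that happened under treatment.

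Two separate problems can follow.

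- **Mediation.** If sorafenib changes the risk of chronic GvHD, and chronic GvHD is related to relapse or death, adjusting for it removes or adds part of the drug's effect. The result is at best a direct effect holding GvHD constant. That is not the comparison implied by the intention-to-treat statement.
- **Immortal time.** If the covariate is a fixed ever/never variable, a patient must stay event-free long enough to develop GvHD. The ever group then looks protected even when GvHD does nothing. If the arms differ in GvHD frequency, this false protection leaks into the treatment coefficient.

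At stake is the reading of the only covariate-adjusted efficacy analysis in the protocol. If it disagreed with the log-rank result, one could not tell whether prognostic imbalance or the adjustment itself was the cause.

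**Working it through.** **1. The plan's own figures (section 11.2).** These fix the baseline hazard for the illustration.

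- Hazard ratio (HR) = ln(0.825)/ln(0.65) = 0.4466, stated as 0.45.
- Schoenfeld's formula at this ratio, two-sided 5%, 80% power and 1:1 allocation gives 49 events, as stated.
- Expected events in 184 patients: 92 × 0.35 + 92 × 0.175 = 32.2 + 16.1 = 48.3, close to 49.
- 184/0.92 = 200 patients.

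None of these uses the Cox covariates, so none depends on this point.

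**2. Timing of the covariates.**

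| Covariate | When its value is known |
|---|---|
| Flt3-ITD ratio | At diagnosis |
| Flt3 inhibitor before transplant | Before transplant |
| Chronic GvHD | Any time; no limit to status at randomisation |

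**3. Illustration of size.** From the protocol: placebo hazard −ln(0.65)/24 = 0.0179 per month, and 1:1 allocation. Assumed, because the documents give no figures: the chronic GvHD rates, the drug's effect on them, and the effect of GvHD on the RFS hazard.

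First set-up: 20,000 patients per scenario, follow-up to 24 months, constant hazards, and a 24-month chronic GvHD risk of 40% on placebo. In A to D, GvHD halves the event hazard. Monte Carlo error on the HR is about 0.02 to 0.03. Entries are treatment HRs.

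| Scenario | No GvHD term | Fixed ever/never | Time-dependent |
|---|---|---|---|
| A. Direct HR 0.45; GvHD 40% in both arms | 0.45 | 0.45 | 0.45 |
| B. Direct HR 0.45; drug raises GvHD to 60% | 0.42 | 0.55 | 0.45 |
| C. Direct HR 0.45; drug lowers GvHD to 20% | 0.48 | 0.40 | 0.45 |
| D. No direct effect; drug raises GvHD to 60% | 0.91 | 1.15 | 0.97 |
| E. Neither drug nor GvHD affects RFS; drug raises GvHD to 60% | 1.05 | 1.25 | 1.05 |
| F. As E, plus an unmeasured common cause of GvHD and RFS | 0.98 | 1.05 | 0.93 |

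- The column without GvHD estimates the total effect. In B and C neither adjusted column matches it: time-dependent coding returns the direct effect of 0.45.
- In E the true ratio is 1; 1.05 is simulation error. Fixed coding still moves the estimate to 1.25, and GvHD itself shows a spurious HR of 0.39.
- In F time-dependent coding moves the estimate too, because conditioning on GvHD opens a path through the common cause.

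Second set-up: 60,000 patients per scenario, GvHD onset within 12 months at 50% risk on placebo, GvHD halving the hazard, direct HR 0.45, fixed coding.

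- GvHD rate multiplied by 1.5: 0.43 without the term, 0.50 with it.
- GvHD rate multiplied by 0.67: 0.48 without, 0.43 with.
- A separate run of the first case at 30% risk gave 0.43 and 0.47.
- With no true GvHD effect, the fitted GvHD HR was 0.60 to 0.70, so the size of this artefact depends on the onset model.

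**4. Rejection rates at the planned size.** 184 patients, 400 runs, no effect of drug or GvHD on RFS, fixed coding. Nominal 5% rejection of the treatment term, without and then with the GvHD covariate: 3% and 3% if GvHD is equal in both arms; 6% and 11% if the drug raises it to 60%; 5% and 7% if the drug lowers it to 20%. Monte Carlo standard error is about 1 to 1.6 percentage points.

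**5. Against sampling error.** With 49 events the standard error of the log HR is about 2/√49 = 0.29. The shifts when GvHD is raised are ln(0.50/0.43) = 0.15 and ln(0.55/0.42) = 0.27, roughly half to nearly all of one standard error.

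**The case against.** The strongest reply is that the distortion is conditional and falls on a supportive analysis. This stands. In scenario A the treatment HR does not move, so a reader who infers that the adjusted effect is biased whatever sorafenib does to GvHD goes too far.

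Second, section 11.4 does not state the coding. A time-dependent covariate fits the same words, and the choice may lie in a statistical analysis plan that is not at hand. Immortal-time bias therefore cannot be asserted as a fact of the plan. This too stands, but it does not rescue the covariate: time-dependent coding still conditions on a variable that treatment may influence.

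Third, the protocol does not say that it expects sorafenib to change chronic GvHD. Section 3.4 reports limited experience. Section 6.1.2.3 says only that it may alter immune cells, and concerns donor lymphocyte infusion, which is not part of the trial. Section 3.3 speaks of GvL. No objective in section 4.1 names GvHD. The documents support an open question about the drug's effect, and an open question is reason enough not to condition on it.

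Fourth, the documents give no onset times for chronic GvHD, and patients with controlled GvHD may enter. The share arising after randomisation is unknown; that some can arise then is enough for the point.

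Two wider inferences should not be drawn. Section 4.1.2 includes the objective "To longitudinally evaluate biomarkers associated with Sorafenib treatment response and Sorafenib resistance and correlation with RFS and OS", and 11.4 sends the other secondary objectives to Kaplan-Meier and log-rank. A reader might conclude that later biomarker values will be compared from randomisation, but that sentence is a general one and does not say so. Section 5.1 admits patients transplanted for refractory disease "or for consolidation in first or second complete remission". A reader might call the absence of disease status from the model an error. The protocol does not rank that factor, and omitting a baseline covariate from a randomised comparison is a choice, not a mistake.

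**Conclusion.** The point holds in a limited form. As written, section 11.4 conditions the adjusted RFS and OS effects on a variable that can arise during treatment, and describes the analysis as intention to treat. If sorafenib changes chronic GvHD, and GvHD is related to outcome or is coded as ever/never, the adjusted HR is not the total effect.

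Under the assumed rates, with fixed coding and a direct HR of 0.45, the shift is from about 0.42-0.43 to 0.50-0.55 if GvHD rises and from about 0.48 to 0.40-0.43 if it falls. There is essentially none if GvHD is unchanged. Time-dependent coding gives a smaller departure: 0.45 against totals of 0.42 and 0.48. The reversal of direction in scenario D requires no direct drug effect and that coding, so it is an extreme case.

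A reader might infer that the trial's main conclusion is at risk. It is not: the log-rank tests of RFS and OS, the 49 events, the 200 patients and the sample-size adaptation do not use this covariate. The text should be corrected, but the trial's validity does not depend on it.

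**What to change.** In section 11.4, delete chronic GvHD from the covariates of the Cox models that estimate the treatment effect, or restrict it to chronic GvHD present at randomisation. State that these models adjust only for values known at randomisation; the Flt3-ITD ratio at diagnosis and Flt3-inhibitor treatment before transplant both qualify.

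Analyse chronic GvHD arising after randomisation separately, as a time-dependent covariate or from a landmark, and label that analysis exploratory.

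The cost is about one sentence. Deletion needs no new data. The restricted version needs chronic GvHD status at randomisation on the case report form; Table 6 has no GvHD row, so this should be confirmed, although the GvHD exclusion already requires an assessment at that time. Event count, sample size and log-rank tests do not change. The only loss is that the association of GvHD with outcome becomes exploratory.
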